Data will be in the form of registry data provided from the US and UK CF registries from the period 2007-2017. These datasets will be provided as encrypted data via the registries preferred data sharing platform (Box.com or similar). Both registries have already reviewed and approved the sharing of their data for use within this project.

Criteria for terminating the registry data

No data will be archived in a data repository following project completion due to the requirements of the CF Foundation and CF Trust registries. The CF foundation considers the project to be completed after 3 years. After this time data files and any copies of the files will be destroyed. The CF Foundation will be provided with written confirmation of destruction of the data and completion of the project or alternatively provided with a sufficient justification for continuation of the project if required. The CF Foundation maintains copies of all data sets sent to researchers and can provide the data again if required for auditing purposes. The CF Trust requires all data to be destroyed at the end of the project and that all data forms must be permanently destroyed within 12 months of the date of supply unless approval has been granted by the UK CF Registry Research Committee for an extension.

STATISTICAL ANALYSIS

Data will be provided from the UK and US registries as an encrypted file and analysis will be performed using Stata software. Statistical analysis will be completed by members of the research team, led by [name]. A full plan for statistical analysis is described below.

[figure not shown]
Objective 1: Assess the rate of PERT use and the incidence of DIOS in UK and US registries 2007-2017

1. Descriptive analysis 2007-2017 to include:
 - Yearly cumulative incidence of DIOS and prevalence of PERT usage in the UK and US (2007-2017)
 - PERT use will be dichotomised (i.e use/no use)
 - Incidence of DIOS (event/no event)
 - **Plotted by year**, separated by registry
 - Stratification by age range (<6, 6-11, 12+)

- Patient demographics of DIOS and PERT reporting
 - The distribution of yearly reported incidence events and use prevalence (%) will be addressed according to age groups, sex, BMI, ethnicity, antibiotic use, comorbidities (including Pseudomonas colonisation, GI complication history, GI co-morbidities such as CFRD and CFRLD), FEV₁ lung function, centre (where available, pseudo ID).

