Trends in the registries will be described, however no statistical tests will be used to directly similarities and differences between the registries over time due to the distinctions between the two registries.

2. The patient demographics lists above will be used for demographic propensity matched controls
 - Patient-level data will be used to create registry-based control groups with similar demographic features to those taking CFTR modulators. Due to the restricted genotype eligibility criteria for the earliest CFTR modulator, Ivacaftor, the CFTR user group may have distinct features compared to the overall registry. In addition the restrictive indications for the use of Ivacaftor and limited number of DIOS events on the registry will therefore mean the number of events within exposed individuals may be low. Therefore propensity scores will be used to define a control group of non-eligible non-users that are otherwise representative at the year CFTR modulator exposure was commenced. See directed acyclic graph (DAG) below.
 - Nearest neighbour matching, caliper 0.2 standard deviation, 3:1 ratio of unexposed to exposed will be used for propensity matching. Matching will be performed according to first year of exposure using all pre-exposure information in wide format. Standardised mean difference will be used to check covariate balance between matched and unmatched populations. Average treatment effect of treated will be used to assess matching specification with alternates.

Directed acyclic graph (DAG) for the potential relationship of CFTR modulator and DIOS

Objective 2: Determine the effect of CFTR modulators on DIOS and PERT, using an population-level controlled interrupted time series

This protocol is confidential and the property of the University of Nottingham. No part of it may be transmitted, reproduced, published, or used by others persons without prior written authorisation from the University of Nottingham

Objective 2 will investigate the effect of CFTR modulator intervention on the rate on PERT use and DIOS incidence.

We will test the hypotheses that;

- a) Ivacaftor introduction (2012) in patients with gating mutations lowered the rate of PERT use and the incidence of DIOS in both registries, and that
- b) The introduction of Orkambi (Ivacaftor/Lumacaftor) for those homozygous for F508del mutations in the US (2015) lowered the rate of PERT use and the incidence of DIOS. Specifically, we hypothesise a downward trend, no lag.

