- UK 2012-2017 & US 2012-2017 separately
 - Exposure: ivacaftor (minimum 6 months) vs No modulator (matched)
 - Secondary comparator: ivacaftor alone and lumacaftor/ivacaftor (US only)
- DIOS events:
 - Outcome: Patient-level annualised DIOS event counts
 - Multilevel Poisson Regression model for count data (or negative binomial) by year
 - Incidence rate ratio (frequency of DIOS events)
 - Adjusted analysis for main covariates (DAG – Fig 2), also include history of DIOS as pre-exposure time will not be modelled.
 - Contingency table with χ^2 /fisher if insufficient events for modelling.
- PERT usage:
 - Outcome: Patient-level annualised PERT dosage standardised by weight
 - Secondary: decreased PERT usage vs continued/increased
 - Multilevel linear regression for continuous data
 - Secondary: multilevel logistic regression for dichotomised data
 - Adjusted for main covariates (DAG – Fig 2), also include history of DIOS as pre-exposure time will not be modelled.
- Sensitivity analyses
 - CFTR modulator start year excluded, finite distributed lag (1-3 years).
 - Long run propensity (cumulative 0-3 years), cumulative modulator exposure.

Sample size and justification

N/A.- registry study

ADVERSE EVENTS

This is a registry study therefore there is no individual participant interaction and as such no associated risk or burden for participants in the study. Patient's data will be provided as anonymised data and therefore patient confidentiality will be maintained.

ETHICAL AND REGULATORY ASPECTS

ETHICS COMMITTEE AND REGULATORY APPROVALS

Requests for the data required the approval of the UK CF Trust Registry Steering Committee after reviewing of the programme development grant aims, analysis and plan for publication of results. In the US, the request for registry data was reviewed and approved by the Patient Registry/Comparative Effectiveness Research Committee and was subject to peer review.

The data will be provided from the registries as anonymised data so the individuals cannot be identified. Specifically, the CF Foundation requires that no individually identifiable information from the CF Foundation Patient Registry shall be included in publications and other written products and data must be presented in the aggregate. Both US and UK registries require that all tables or presentation of the data generated from registry data should include a patient count of five or more in each cell and any values less than 5 should be represented as <5.

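### The Objective 3 continuous PERT dose model names history of DIOS, but not prior PERT dose, to stand in for unmodelled pre-exposure time; prior dose should be named in the model and in the matching

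*Combined protocol and SAP*

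**What the plan says.** Under Statistical Analysis, Objective 3, the main PERT outcome is continuous: "Outcome: Patient-level annualised PERT dosage standardised by weight". It is fitted by multilevel linear regression over 2012-2017, separately for each registry. The adjustment line reads "Adjusted for main covariates (DAG – Fig 2), also include history of DIOS as pre-exposure time will not be modelled". The DIOS model a few lines above has nearly the same line: "Adjusted analysis for main covariates (DAG – Fig 2), also include history of DIOS as pre-exposure time will not be modelled".

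Two other places decide what else is controlled.

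- **The DAG.** Its caption is "Directed acyclic graph (DAG) for the potential relationship of CFTR modulator and DIOS". The figure is not visible in the text reviewed.
- **The matching (Objective 1, item 2).** One sentence says "The patient demographics lists above will be used for demographic propensity matched controls". That list describes DIOS and PERT reporting "according to age groups, sex, BMI, ethnicity, antibiotic use, comorbidities", then FEV1 and centre; it names no PERT use or dose as a matching variable. A later sentence is broader: "Matching will be performed according to first year of exposure using all pre-exposure information in wide format". Balance is to be checked: "Standardised mean difference will be used to check covariate balance between matched and unmatched populations".

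PERT dosage and usage are among the requested variables (Study Design). Data start in 2007, to give at least 4 years before ivacaftor.

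**The concern.** The reason given for adding a history term, that pre-exposure time is left out of the model, applies to both outcomes. In the DIOS model the added term is the outcome's own earlier value. In the PERT model it is the earlier value of a different outcome. Earlier PERT dose would normally be the strongest single predictor of later dose, and it is not mentioned.

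Two things are at stake. If prior dose is neither matched on nor among the DAG covariates, any lasting dose difference between modulator users and genotype-ineligible controls would enter the estimated effect. A random patient intercept would not remove it, because only 2012-2017 is modelled. If prior dose is matched on, that bias is already dealt with as far as prior dose can do it, but a model without prior dose still gives wider intervals than necessary and a standard error that ignores the balance achieved by matching.

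**Working it through.** The plan states no sample size, SD, correlation or effect size for this outcome, so there is no figure to reproduce. The calculation shows what prior dose could contribute over a range of assumed inputs.

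**From the documents:** 2012-2017 allows up to m = 6 outcome years; at least k = 4 pre-exposure years for a 2012 starter; 3:1 nearest-neighbour matching with caliper 0.2 SD.

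**Assumed:** yearly dose with SD 1; year-to-year correlation r = 0.5 or 0.8, either constant or decaying as AR(1); m = 3 or 6; no other covariates.

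**Method.** Let y be the mean dose over m outcome years, x1 the dose in the last pre-exposure year and x2 the mean of the three earlier years. With b = Sxx⁻¹Sxy:

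- variance cut = b′Sxy / Var(y)
- reduction in interval width = 1 − √(1 − cut)
- share of a constant group difference left = 1 − (b1 + b2)

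Under constant correlation the two terms act together as the 4-year mean x̄, with Var(x̄) = (1 + 3r)/4 and Var(y) = (1 + (m − 1)r)/m. So cut = r² / [Var(y)·Var(x̄)] and share left = 1 − r/Var(x̄). For r = 0.5, m = 3: cut = 0.25/(0.6667 × 0.625) = 0.60; share left = 1 − 0.5/0.625 = 0.20.

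Under AR(1) the earlier mean gets zero weight and b1 = (r + … + r^m)/m. For r = 0.5, m = 3: b1 = 0.875/3 = 0.292, Var(y) = 5.5/9 = 0.611, cut = 0.292²/0.611 = 0.139; share left = 0.71.

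| Structure | r | m | Variance cut | Width falls | Difference left |
|---|---|---|---|---|---|
| Constant | 0.5 | 3 | 60% | 37% | 20% |
| Constant | 0.5 | 6 | 69% | 44% | 20% |
| Constant | 0.8 | 3 | 87% | 64% | 6% |
| Constant | 0.8 | 6 | 90% | 69% | 6% |
| AR(1) | 0.5 | 3 | 14% | 7% | 71% |
| AR(1) | 0.5 | 6 | 7% | 4% | 84% |
| AR(1) | 0.8 | 3 | 51% | 30% | 35% |
| AR(1) | 0.8 | 6 | 36% | 20% | 51% |

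If the planned covariates explain 20% of dose variance (assumed), the residual correlation is (r − 0.2)/0.8 = 0.375 or 0.75. The cut at m = 3 is then 45-83% (constant) or 7-42% (AR(1)).

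**If yearly doses are already in the propensity score.** A simulation used 300 exposed, a pool of 6,000, five other covariates, m = 3, true effect 0 and 300 datasets per scenario (all assumed).

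- *Bias:* with a constant difference of −0.30 SD, the estimates without and with the two terms are −0.063 and −0.061 (constant, r = 0.5), −0.019 and −0.017 (constant, 0.8), −0.215 and −0.215 (AR(1), 0.5), −0.104 and −0.103 (AR(1), 0.8). The terms add almost nothing.
- *Calibration:* with no difference and no prior dose in the model, model SE against true SD is 0.0545/0.0363 = 1.50 and 0.0621/0.0354 = 1.75 (constant), 0.0522/0.0463 = 1.13 and 0.0609/0.0484 = 1.26 (AR(1)). With the two terms the ratios are 1.07, 0.93, 1.07 and 0.98.
- *True precision:* sampling variance falls by 1 − (0.0322/0.0363)² = 21% and 1 − (0.0241/0.0354)² = 54% (constant), and by 4% and 20% (AR(1)).

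Each true SD carries about 4% Monte Carlo error, so the AR(1), r = 0.5 results are small and imprecise.

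**The case against.** The strongest reply is that the plan probably handles this already. Read literally, matching on everything known before exposure, one column per year, includes yearly PERT dose, since dose is a requested variable. The narrower list was written for description. The DAG may contain PERT, and a figure that cannot be seen is not missing from the plan. The history-of-DIOS phrase adds to the covariate set and does not close it. On this reading only precision remains, and an overstated standard error is a conservative fault.

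Much of that stands, and it rules out a stronger conclusion. A reader might infer that the PERT estimate is biased, or that baseline dose was forgotten. The documents support neither: that would need prior dose to be absent from both the matching and the DAG, and a group difference that no document shows. With an assumed imbalance of 0.2 SD carried forward at correlation 0.7 and 200 exposed, one can calculate a false-positive rate of about 38-41%, but nothing in the plan supplies that imbalance.

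The reply does not remove the point. The same broad matching clause would also cover DIOS history, and GI complication history is in the named list, yet the plan still adds DIOS history to the outcome model. By its own logic, matching does not replace a baseline term.

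Two further objections are fair. Covariate adjustment does not fully remove a constant difference, as the table shows. The plan also has PERT analyses that use earlier dose or earlier years: the Objective 2 interrupted time series and the Objective 3 secondary decreased-dose outcome. Those use yes/no outcomes, however, and do not repair the continuous model.

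**Conclusion.** The point holds as a gap in the adjustment of one model. The continuous PERT dose model names another outcome's baseline and not its own, and the text does not settle whether matching or the DAG supplies it.

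What holds whether or not prior dose is matched on is better precision and better-calibrated standard errors. The gain runs from small (7% variance cut, AR(1), r = 0.5, six outcome years) to large (90%, constant correlation, r = 0.8, six years). That width reflects the lack of any dose correlation in the documents. If dose is already matched on, part of the narrowing only corrects an overstated standard error, and the true variance gain is smaller.

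The bias part is conditional. If prior dose is not controlled elsewhere and a lasting group difference exists, the fix leaves 6-20% of it under constant correlation and 35-84% under AR(1), against 100% without the fix if the other covariates remove none of it. The case for acting rests on the low cost and on a benefit under either reading, not on demonstrated bias.

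**What to change.** 1. **Outcome model.** In the Objective 3 continuous-dose model, keep history of DIOS and add three terms: weight-standardised PERT dose in the last pre-exposure year, mean dose over the earlier available pre-exposure years, and PERT user status before exposure. Controls take the index year of their matched exposed patient. This also fixes the baseline year for users who start after 2012, whose pre-start years fall inside the analysis window.
2. **Matching.** Name prior PERT dose and user status in the propensity score, and report their standardised mean differences in the balance check already planned. State whether the DAG covariates for the PERT model include them.
3. **Patients without a prior dose.** Code true non-users as dose zero with user status no. Treat patients with no pre-exposure registry year (for example the very young) separately from users whose dose was not recorded; a single indicator would merge the two. Run a sensitivity analysis restricted to patients with a recorded prior dose, in addition to any indicator and not in place of it.

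The cost is SAP wording and a few covariates in one model; PERT dosage is already requested for 2007-2017. The drawback is that some patients will lack a prior dose, and the documents do not say how completely either registry records it.
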